4.3 Secondary Objectives

none

4.4 Safety Objectives

No short-term risks other than those discussed so far are to be expected in this study.

SUPSI

5. STUDY OUTCOMES

5.1 Primary Outcome

Jump height measurement

The jump height after exercise is determined using a specially designed jump height measuring plate (Just Jump Plate, Probotics Inc., Huntsville, USA). The test subjects assume a standing position on the plate. They are allowed to start from a squatting position to measure the jump height (countermovement jump). The arms must be positioned at the hips during the entire movement. The measurement take place directly, 24 hours, 48 hours and 72 hours after the intervention.

Muscle activity (MVIC)

MVIC is performed on the Cor 1 – ergometer chair for biomechanical measurements V1.0 and is expressed in kg (www.otbioelettronica.it). The conduction velocity is measured using the surface electromyogram system EMG-USB2 from OT Bioelettronica ([otbioelettronica.it](http://www.otbioelettronica.it)), bandpass filtered between 10-750Hz and rectified (full-wave rectify). MVIC is measured on the Cor 1 ergometer chair in 90° knee flexion. The raw data of muscle activity to measure conduction velocity is processed using OT Bioelettronica software (MISO II). The electrodes are placed according to the guidelines of Barbero et al. (2012) "Atlas of Muscle Innervation Zones". The measurement takes place immediately, 24 hours, 48 hours and 72 hours after the intervention.

Muscle swelling

Muscle swelling of the thigh is measured by ultrasound imaging (MyLabClassC, Esaote, Genoa, Italy). The images were evaluated using the OsiriX DICOM viewer software (OsiriX, Pixmeo SARL, Switzerland). The measurement takes place before, directly, 24 hours, 48 hours and 72 hours after the intervention.

Oxygen saturation of the blood

The oxygen saturation of the blood is measured with a portable pulse oximeter with a finger clip probe (Nonin 7500, Nonin medical B.V., Plymouth, USA). This measurement takes place during the baseline measurements as well as during the jump protocol.

Figure: Measurement of the oxygen content of the blood

Oxygen saturation of the muscle

The oxygen saturation (%) of the thigh muscles is measured with the tissue oxygenation monitor using near-infrared spectroscopy (moorVMS-NIRS, moor instruments, www.moore.co.uk). The measurement is non-invasive and takes place via near-infrared light. The sensors are fixed around the corresponding

SUPSI

muscles. The muscle oxygen saturation measurement is taken directly and 24, 48 and 72 hours after the intervention.

Figure: Measurement of the oxygen saturation of the muscle

Heart rate

The heart rate is determined by means of a heart rate monitor with a chest strap (Polar T31, Polar Inc. Kempele, Finland). Blood pressure and heart rate are measured directly and 24, 48 and 72 hours after the intervention.

Skin temperature

Skin temperature is measured via the iButton system (www.ibuttonlink.com). The self-adhesive sensors transmit the information about the skin temperature wirelessly to a computer. Furthermore, the skin temperature is recorded using a thermal imaging camera (A655 sc series, FLIR, InfrarotTec Systems, Ranstadt, Germany). The Skin temperature is measured directly and 24, 48 and 72 hours after the intervention. The iButtons are attached to the following locations using a tape strip: centre of the shoulder blade, neck (6th cervical vertebra), back of the hand, centre of the shin and centre of the thigh. The iButtons are removed from the affected areas during the cold water bath or hot water bath and then reattached.

Core Body Temperature

The core body temperature is determined via the e-Celsius® performance (<https://www.bodycapmedical.com>). With the help of this ingestible capsule, the core body temperature is continuously monitored, recorded and transmits the data wirelessly to a monitor (BodyCAP medical, Hérouville Saint-Clair, France). Core body temperature is measured directly and 24, 48 and 72 hours after the intervention.

Inflammation parameters

The measurement of inflammatory parameters such as creatine kinase (CK), interleukin 6 (IL6) or C-reactive protein (CRP) is carried out via a venous blood sample of approx. 6ml (Accutrend, Roche Diagnostic, Rotkreuz, Switzerland & Reflotron, Roche Diagnostic, Rotkreuz, Switzerland). The measurement takes place directly, 24 hours, 48 hours and 72 hours after the intervention by trained specialists.

SUPSI

Subjective information on breathlessness

The subjects indicate their subjective feeling of breathlessness on a modified BORG scale (0 – 10). The scale will be scaled from "0" (no shortness of breath at all) to "10" (maximum breathlessness). The measurement takes place before the intervention.

Subjective information on general exhaustion

The subjects indicate their subjective general feeling of exhaustion on a BORG scale (6 – 20). The scale will be scaled from "6" (very, very light load) to "20" (very, very strenuous load). The measurement takes place before the intervention.

Subjective muscle soreness

The subjects reported their subjective feeling of muscle soreness on a visual analogue scale (VAS). The scale will be scaled from "0" (no muscle soreness present) to "10" (greatest imaginable muscle soreness) in cm increments. The measurements are take immediately, 24 hours, 48 hours and 72 hours after the intervention.

Thermal comfort and temperature sensation

This parameter is measured using a scale. The test subjects indicate their subjective temperature perception on a 9-point scale from -4 (very cold) to +4 (very hot). They then rate the thermal comfort between 0 (pleasant) and 4 (extremely unpleasant) on a 5-point scale. These measurements are taken before and after the intervention.

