	
Subjective information on shortness of breath
 
The subjects reported their subjective shortness of breath on a BORG scale (0 – 10). The scale will be scaled from "0" (no shortness of breath at all) to "10" (maximum shortness of breath). The measurement takes place before the intervention.
 
Thermal comfort and temperature sensation
 
These parameters are measured using a scale. This measurement is carried out before and after the intervention.
 
Further processing of the data
 
For further data analysis, the software MATLAB® will be used, while Excel from Windows® will be used for data pooling and for the graphical representation of the end data. All digital documents are password-protected. Paper data is stored in a separate, lockable filing cabinet. The data collected with Excel is given version numbers and stored in read-only mode. The corresponding versions are printed out, signed by the director of studies and filed in the above-mentioned filing cabinet. Only the director of studies has access to this filing cabinet.

Study Product / Intervention:	
The Aspen inflatable whirlpool (NETSPA) is a certified product that complies with European regulations, directives and standards. 2006/95/EC Low Voltage Directive, 2004/108/EC (Electromagnetic compatibility), 2011/65/EU (restriction of the use of certain Substances in appliances), 2009/125/EC (ecodesign of energy-related products). All guidelines are in writing in the Operations Manual Chapter 1 (page 40). In the inflatable whirlpool, temperatures of 40°C are generated with the help of a heating motor. The whirlpool is already commercially available and is used in the private wellness area.
 
Simulated altitude training is quickly becoming the most promising development in the world in terms of athletic performance and peak fitness. With the Cloud 9, a simulated altitude of up to 4000 m above sea level can be achieved. This corresponds to an oxygen partial pressure of 12.7 %. The Cloud 9 altitude training device is designed for all levels of athletes (including amateurs) who want to improve their performance. The Cloud 9 is a solid, certified product that complies with the European Directives on Electromagnetic Compatibility, Machinery Directive, Air Pressure Equipment and Low Voltage Equipment (89/336/EEC, 91/368/CEE, 93/68/CEE, 97/23/EC, EN61010-1).

SUPSI

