4.2 Primary Objective

In this project, the effect of post-activity cooling or warming on physiological and psychological recovery parameters is measured and compared to the hypoxia intervention and the passive control group.

Physiological measurements

- Jump height measurement (cm)
- Maximum voluntary isometric thigh contraction (kg)
- Muscle swelling (mm)
- Blood oxygen saturation (%)
- Oxygen saturation of the muscles (%)
- Heart rate (bpm)
- Skin temperature (°C)
- Core Body Temperature (°C)
- Inflammation parameters; IL6 (pg/ml), CRP (mg/dl), creatine kinase (U/L)

Psychological measurements

- Dyspnea questionnaire (mod. Borg scale)
- Exhaustion questionnaire (Borg scale)
- Subjective muscle soreness (VAS scale)
- Thermal comfort and thermal sensation

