9. STUDY ASSESSMENTS

9.1 Study flow chart(s) / table of study procedures and assessments

The test subject information is sent to the test subjects' homes in advance or given to them personally

1. Subject Information & Informed Consent

30 min (questions and ambiguities will be discussed individually)

2. Preparation of the test person

15 min

3. Executing the test protocol

SUPSI

Test protocol: Time required – maximum 255 min			
Cold Water Immersion vs. Hot Water Immersion vs. Hypoxia Group vs. Passive Control Group			
Cold water immersion 1.) Baseline Informed consent, written consent, review of inclusion/exclusion criteria, health questionnaire, pregnancy test Heart rate Skin/ core body temperature Oxygen saturation (blood, muscle) Inflammation parameters VAS & BORG thermal comfort and thermal sensation US 3 x Vertical Jumps 3 x MVIC =30 min	Hot water immersion 1.) Baseline Informed consent, written consent, review of inclusion/exclusion criteria, health questionnaire, pregnancy test Heart rate Skin/core body temperature Oxygen saturation (blood, muscle) Inflammation parameters VAS & BORG thermal comfort and thermal sensation US 3 x Vertical Jumps 3 x MVIC =30 min	Hypoxia Intervention 1.) Baseline Informed consent, written consent, review of inclusion/exclusion criteria, health questionnaire, pregnancy test Heart rate Skin/core body temperature Oxygen saturation (blood, muscle) Inflammation parameters VAS & BORG thermal comfort and thermal sensation US 3 x Vertical Jumps 3 x MVIC =30 min	Passive Control Intervention 1.) Baseline Informed consent, written consent, review of inclusion/exclusion criteria, health questionnaire, pregnancy test Heart rate Skin/core body temperature Oxygen saturation (blood, muscle) Inflammation parameters VAS & BORG thermal comfort and thermal sensation US 3 x Vertical Jumps 3 x MVIC =30 min
2.) Jump protocol 5 x 20 max vertical jumps after 30sec Heart rate Skin/ core body temperature	2.) Jump protocol 5 x 20 max vertical jumps after 30sec Heart rate Skin/ core body temperature	2.) Jump protocol under hypoxia 5 x 20 max vertical jumps after 30sec Heart rate Skin/ core body temperature	2.) Jump protocol 5 x 20 max vertical jumps after 30 sec Heart rate Skin/ core body temperature

SUPSI

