Oxygen saturation (blood, muscle) Mod. BORG & BORG =30 min	Oxygen saturation (blood, muscle) Mod. BORG & BORG =30 min	Oxygen saturation (blood, muscle) Mod. BORG & BORG =30 min	Oxygen saturation (blood, muscle) Mod. BORG & BORG =30 min
3.) Cold water immersion 10 min at 10°C Heart rate Skin/core body temperature Oxygen saturation (muscle) Thermal comfort and Temperature sensation =10 min	3.) Hot water immersion 10 min at 40°C Heart rate Skin/core body temperature Oxygen saturation (muscle) Thermal comfort and Temperature sensation =10 min	3.) Passive supine position 10 min at room temperature Heart rate Skin/core body temperature Oxygen saturation (muscle) Thermal comfort and Temperature sensation =10 min	3.) Passive supine position 10 min at room temperature Heart rate Skin/core body temperature Oxygen saturation (muscle) Thermal comfort and Temperature sensation =10 min
4.) Follow-up immediately after the intervention Heart rate Skin/core body temperature Oxygen saturation (blood, muscle) Inflammation parameters US VAS & BORG 3 x Vertical Jumps 3 x MVIC =30 min	4.) Follow-up immediately after the intervention Heart rate Skin/core body temperature Oxygen saturation (blood, muscle) Inflammation parameters US VAS & BORG 3 x Vertical Jumps 3 x MVIC =30 min	4.) Follow-up immediately after the intervention Heart rate Skin/core body temperature Oxygen saturation (blood, muscle) Inflammation parameters US VAS & BORG 3 x Vertical Jumps 3 x MVIC =30 min	4.) Follow-up immediately after the intervention Heart rate Skin/core body temperature Oxygen saturation (blood, muscle) Inflammation parameters US VAS & BORG 3 x Vertical Jumps 3 x MVIC =30 min

SUPSI

5.) Cold water immersion 10 min at 10°C Heart rate Skin/core body temperature Oxygen saturation (muscle) Thermal comfort and thermal sensation =10 min	5.) Hot water immersion 10 min at 40°C Heart rate Skin/core body temperature Oxygen saturation (muscle) Thermal comfort and thermal sensation =10 min		

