6.-8.) Follow up 24, 48 and 72 hours after the intervention Heart rate Skin/ core body temperature Oxygen saturation (blood, muscle) Inflammation parameters US VAS & BORG 3 x Vertical Jumps 3 x MVIC =30 min per follow-up	6.-8.) Follow up 24, 48 and 72 hours after the intervention Heart rate Skin/ core body temperature Oxygen saturation (blood, muscle) Inflammation parameters US VAS & BORG 3 x Vertical Jumps 3 x MVIC =30 min per follow-up	5.-7.) Follow up 24, 48 and 72 hours after the intervention Heart rate Skin/ core body temperature Oxygen saturation (blood, muscle) Inflammation parameters US VAS & BORG 3 x Vertical Jumps 3 x MVIC =30 min per follow-up	5.-7.) Follow up 24, 48 and 72 hours after the intervention Heart rate Skin/core body temperature Oxygen saturation (blood, muscle) Inflammation parameters US VAS & BORG 3 x Vertical Jumps 3 x MVIC =30 min per follow-up

SUPSI

Test protocol	Time exposure	Visits
Information, written consent, examination of inclusion/ exclusion criteria, health questionnaires, pregnancy test, detection of adverse events	30min + 15min	Unique
Baseline, recording of adverse events	30min	Unique
Jump log, recording of adverse events	30min	Unique
Cold water immersion, recording of adverse events	20min + 130min (3x30min) = 150min	Unique
Hot water immersion, recording of adverse events	20min + 130min (3x30min) = 150min	Unique
Hypoxia group, recording of adverse events	20min + 120min (3x30min) = 140min	Unique
Control group, recording of adverse events	20min + 120min (3x30min) = 140min	Unique
Total time spent	245min or 255min	

SUPSI

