H1 Skin temperature is increased by hot water immersion compared to cold water immersion, hypoxia group and passive control group during 72 hours.

Core Body Temperature (°C)

H0 Core body temperature is not increased by hot water immersion compared to cold water immersion, hypoxia group, and passive control group during a 72-hour recovery period.

H1 Core body temperature is increased by hot water immersion compared to cold water immersion, hypoxia group and passive control group during 72 hours.

Inflammation parameters (CRP, IL6, CK)

H0 Inflammation levels are not increased by hot water immersion compared to cold water immersion, hypoxia group, and passive control group during a 72-hour recovery period.

H1 The inflammation rates are increased by hot water immersion compared to cold water immersion, hypoxia group and passive control group during 72 hours.

Subjective information on shortness of breath (mod. BORG)

H0 Subjective information on shortness of breath is not increased by hot water immersion compared to cold water immersion, hypoxia group and passive control group during a 72-hour recovery period.

H1 The subjective information on shortness of breath is increased by hot water immersion compared to cold water immersion, hypoxia group and passive control group during 72 hours.

Subjective data on general exhaustion (BORG)

H0 The subjective data on general fatigue are not increased by the hot water immersion compared to the cold water immersion, hypoxia group and passive control group during a 72-hour recovery period.

H1 The subjective data on general fatigue are increased by the hot water immersion compared to the cold water immersion, hypoxia group and passive control group during 72 hours.

Subjective muscle soreness (VAS)

H0 Subjective muscle soreness is not increased by hot water immersion compared to cold water immersion, hypoxia group, and passive control group during a 72-hour recovery period.

H1 Subjective muscle soreness is increased by hot water immersion compared to cold water immersion, hypoxia group and passive control group during 72 hours.

SUPSI

Thermal comfort and temperature perception

H0 Thermal comfort and temperature perception are not increased by hot water immersion compared to cold water immersion, hypoxia group and passive control group during a 72-hour recovery period.

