11.4.2 Primary Analysis

The statistical data analysis will be carried out by [name] once the data collection for the entire project has been completed.

Repeated measures analysis of variance (MANOVA)

2 factors:

Factor 1: Intervention (cold water immersion vs. hot water immersion vs. hypoxia group vs. passive control intervention)

Factor 2: Time (Baseline, 0, 24 hours, 48 hours, 72 hours)

The significance level is set at $P < 0.05$, and the statistical data analysis is carried out with SPSS 27.

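### Dyspnoea is a primary outcome with a 72-hour hot-water hypothesis, but its own timing text and the flow chart schedule it only before the first bath, and the Aim in 3.1 implies later readings

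*Combined protocol and SAP*

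**What the plan says.** **Status.** The synopsis and section 4.2 list "Dyspnea questionnaire (mod. Borg scale") among the primary measurements. There are no secondary outcomes.

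**Hypothesis.** Section 11.1 states: "The subjective information on shortness of breath is increased by hot water immersion compared to cold water immersion, hypoxia group and passive control group", over 72 hours.

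**Analysis.** Section 11.4.2 crosses four groups with "Factor 2: Time (Baseline, 0, 24 hours, 48 hours, 72 hours"). No outcome is exempted.

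**Timing in the outcome text.** The synopsis entry ends "maximum shortness of breath). The measurement takes place before the intervention". The entry in 5.1 ends "maximum breathlessness). The measurement takes place before the intervention", and 9.2.1 repeats it.

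**Timing in the flow chart (9.1).** The modified Borg appears once per arm, at step 2 (jump protocol): "Oxygen saturation (blood, muscle) Mod. BORG & BORG =30 min". Baseline has "Inflammation parameters VAS & BORG thermal comfort and thermal sensation US 3 x Vertical Jumps 3 x MVIC =30 min". The 24, 48 and 72 hour visits have "Inflammation parameters US VAS & BORG 3 x Vertical Jumps 3 x MVIC =30 min per follow-up". Step 4, immediately after the intervention, likewise lists the VAS and Borg without the modified Borg.

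**Text pointing the other way.** The Aim of the study in 3.1 names shortness of breath as a subjective recovery parameter, then says the parameters are measured directly and at 24, 48 and 72 hours after exercise. The synopsis (Statistical Considerations) and the opening line of 9.2 are general timing sentences that name no outcome.

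**The concern.** A hypothesis about the effect of a bath needs readings after the bath. The two places that staff would use to schedule this rating, the outcome entry and the flow chart, provide none. At the one scheduled reading the hot, cold and control arms have had the same procedures, so a difference between them can only be chance. Only the hypoxia arm differs by then, because it has jumped under hypoxia. A hot-versus-hypoxia difference there would reflect the hypoxia, not the hot bath.

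At stake is one designated primary outcome. A rating not asked at a visit cannot be recovered later.

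**Working it through.** The protocol gives no figure to reproduce here. The check sets the schedules side by side and counts levels.

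| Planned level (11.4.2) | Contact in 9.1 | Modified Borg in flow chart | Outcome text (synopsis, 5.1, 9.2.1) | Aim in 3.1 |
|---|---|---|---|---|
| Baseline | Step 1 | No | Possibly | Not stated |
| none | Step 2, after the jumps | Yes | Compatible, except in the hypoxia arm | Possibly (directly after exercise) |
| 0 | Step 4 | No | No | Possibly |
| 24, 48, 72 h | Follow-up visits | No | No | Yes |

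**Levels available**
- Flow chart: step 2 is neither Baseline (step 1) nor 0 h (step 4), so 0 of 5 planned levels.
- Outcome text: at most Baseline, so 1 of 5, and 0 of 4 post-bath levels.
- Aim in 3.1: 3 of 4 post-bath levels (24, 48, 72 h). Its timing is counted from exercise, so the direct reading may be step 2 rather than step 4.

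**Degrees of freedom**, with 4 groups:
- Planned, 5 levels: Time 5 − 1 = 4; Intervention × Time (4 − 1)(5 − 1) = 12.
- One level: Time 1 − 1 = 0; Intervention × Time (4 − 1)(1 − 1) = 0.

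A one-way comparison of groups at a single reading could still be run, but it would say nothing about the baths.

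**Ratings.** Four post-bath levels need 4 × 40 = 160 ratings at the sample size in 11.2, or 4 × 60 = 240 at the 60 given in 6.1. The outcome text and flow chart yield 0.

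**Share of the hypotheses.** Section 11.1 has 13 hypothesis headings; this is one.

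**Related mismatches**
- *Thermal comfort and sensation* also carry a 72-hour hypothesis in 11.1. The flow chart lists them at steps 1, 3 and 5, and step 5 exists only in the bath arms. With step 4 as the 0 h level, the levels 0, 24, 48 and 72 h are all missing. This conflicts with the before-and-after timing in 5.1 and 9.2.1, and with 3.1, which lists these ratings too.
- *Exhaustion* is timed before the intervention in the synopsis, 5.1 and 9.2.1, but the flow chart and 9.3.2 have it at follow-up.
- *Blood oxygen saturation* is timed at baseline and during the jumps in the synopsis, 5.1 and 9.2.1, but the flow chart also lists it at step 4 and follow-up.

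**The case against.** The best defence is that the follow-up visits do include dyspnoea under another label. The synopsis calls the 0–10 breathlessness scale simply a Borg scale. Section 12.2.1 describes one questionnaire for dyspnoea and stress assessment. The data collection sheet (section 17, item 3) is not in the documents. On this view the Borg entry at step 4 and at follow-up covers both scales. This cannot be excluded, but it is the weaker reading: the outcome lists in the synopsis and 4.2 separate the scales, and step 2 of the flow chart names both. It would also leave the three outcome entries wrong, so a correction is needed either way.

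A second defence is that the timing sentence is unreliable. It is one sentence repeated, not three independent statements, and the same sentence is attached to exhaustion, where the flow chart contradicts it. This stands. For dyspnoea, however, the flow chart agrees with the sentence in giving no later reading.

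A reader might also infer that dyspnoea was deliberately left out of follow-up, because the synopsis objective, 4.1 and 9.3.2 name soreness and exhaustion but not breathlessness. Those lists are not exhaustive, and 9.3.2 also omits blood oxygen saturation, which the flow chart schedules. Little weight should rest on them.

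**Conclusion.** The contradiction is certain on the text and should be fixed. Under the outcome text and flow chart, no post-bath dyspnoea reading exists, the planned group-by-time analysis cannot be fitted for this outcome, and the hypothesis is untestable at any sample size. The effect is confined to one of 13 hypotheses. The thermal hypothesis has a similar gap, four of five planned levels on the flow chart.

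Two stronger readings are tempting. One is that the trial will collect no breathlessness data after the baths. The documents do not establish this: it depends on staff following the specific schedule and on the Borg entry at follow-up meaning only the 6–20 scale. The other is that the general sentences clearly require all four post-bath readings. They do not: 3.1 counts from exercise, the synopsis sentence names no outcome, and the line in 9.2 can be read as deferring to the flow chart.

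**What to change.** Choose one of two repairs for dyspnoea.

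1. **Withdraw it.** Remove dyspnoea from the primary outcomes (synopsis, 4.2, 5.1, 9.2.1), from the hypotheses in 11.1 and from the repeated-measures analysis in 11.4.2. Report the step 2 reading descriptively.
2. **Schedule it.** Add the modified Borg at baseline, step 4 and the 24, 48 and 72 hour visits, where the VAS and Borg are already asked.

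With either choice, align the synopsis (dyspnoea entry and Statistical Considerations), 3.1, 5.1, 9.1, 9.2, 9.2.1 and 9.3.2, and use one fixed name for each scale (modified Borg 0–10, Borg 6–20) throughout, including the data sheet.

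For the thermal ratings, either limit the hypothesis to the acute points collected in all four arms, or add the ratings at step 4 and follow-up. Reconcile the schedules for exhaustion and blood oxygen saturation; the documents do not show which was intended.

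**Cost.** A protocol amendment with prior ethics approval (2.3, 10.4). Option 1 is otherwise wording only. For dyspnoea, option 2 adds five short ratings per participant, 5 × 40 = 200 or 5 × 60 = 300 in all, with no extra visit. Version 06 is dated 28.09.2021, inside the planned May–December 2021 data-collection period, so any participants already measured under the flow chart would lack the added ratings.
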